10.2 SETTINGS

The study will include approx. 4 sites or more, if required (Table 1). Estimated total number of recruited patients is 66. Based on feasibility assessments, approximately 66 patients are expected to qualify for the study and undergo surgery. All patients who undergo surgery will be included in the analysis. An anticipated dropout rate is 10%. Finally, number of subjects eligible for analysis: sample size is expected to be at least 60. The prospective recruitment of patients, by enrolling patients who have planned surgery and meet enrolment criteria will last for 12 months from the study start. All recruited patients will be followed up to 36 months after the date of the surgery.

Note: in emergency situation that requires acute surgery with TachoSil application, obtaining informed consent and including the patient in the study after surgery may be considered, if legal and ethical requirements are met.

The study population is paediatric patients undergoing a cardiovascular, hepatic or other solid organs surgery and polytrauma with injuries of blood vessels, parenchymal organs, lungs requiring the use of drugs for local haemostasis, tissue sealing when control of bleeding by standard surgical techniques (such as suture, ligature, clips or cautery) appeared to be ineffective or impractical.

PasTel

Data will be collected from the following age groups :

- Infants and toddlers (≥ 28 days - < 2 years) on the day of signing the ICF
- Children (≥ 2 years – < 12 years) on the day of signing the ICF
- Adolescents (≥ 12 years – less than 15 years) on the day of signing the ICF

Patient age analysis will be conducted throughout the study to ensure a proportional number of participants in each of the three age groups (if possible, approx. 33% per group). Ensuring an adequate number of participants in each age group will ensure that data are collected across a broad paediatric population to assess short- and long-term safety evaluation.

Inclusion/Exclusion criteria

The study population covers paediatric patients undergoing a cardiovascular, hepatic or other solid organs surgery, and polytrauma patients with injuries of blood vessels, parenchymal organs, lungs requiring the use of drugs for local haemostasis, tissue sealing when control of bleeding by standard surgical techniques (such as suture, ligature, clips or cautery) appeared to be ineffective or impractical (secondary haemostatic treatment).

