Follow-up phase: The study phase is scheduled to last for up to 36 months following the date of surgery for each enrolled patient. There are six planned follow-up visits: one at 1 month (\pm 15 days) after surgery, another at 3 months (\pm 15 days), a third at 6 months (\pm 15 days), and a fourth, fifth and sixth visits at 12, 24 and 36 months (\pm 30 days) post-surgery, respectively. However, to minimize stress for patients and caregivers associated with the study and the surgical intervention itself, the number and frequency of follow-up visits during the observation period can be align with the routine follow-up procedures of the clinical sites.

The follow-up visits can be conducted in person at the study site if such visits are routinely performed, or they can take the form of telephone interviews with the patient and/or patient

PasTel

legal representative conducted by the Investigator. In both cases eCRF should be completed with all collected and required by Protocol data.

Patients have the right to discontinue their participation in the study at any time and for any reason, whether specified or unspecified.

Furthermore, a patient/legal representative (if applicable) may be withdrawn from the study if the Investigator determines that the patient no longer meets any of the inclusion/exclusion criteria.

Lost-to-follow-up (LTFU)

To ensure the smooth progress of the PasTel study, it is crucial to minimize the occurrence of lost-to-follow-up (LTFU). Loss-to-follow-up refers to patients and/or their legal representative who, at some point during the study, cannot be reached for further follow-up procedures, resulting in an unknown status and the inability to collect important long-term information, including adverse events. On the other hand, "dropout" refers to patients who voluntarily withdraw from the study, with their health status known upon departure.

To minimize lost-to-follow-up, the following follow-up process will be implemented: If a study participant (or their legal representative) does not respond to the initial telephone contact, up to two reminder calls will be made. If there is still no response after three phone calls, the participant will be sent an email or certified letter. The overall objective is to keep the loss-to-follow-up rate below 10 %. Based on the Corza Medical experience and Feasibility analysis, it is anticipated that the final LTFU will be approximately 10 %.

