- Adverse Events of Special Interest evaluation including treatment of AESIs
- Comorbidities and their evaluation for the assessment of adverse events (AEs / AESI)
- Granuloma occurrence and Tissue adhesions and other clinically significant events for the endpoint
- Vital signs (as per each site's standard of care as blood pressure, body temperature, and heart rate), if available
- Laboratory data (as per each site's standard of care such as: blood count, C-reactive protein [CRP], International Normalized Ratio[INR], Activated Partial Thromboplastin Time [APTT]),if available

Follow-up visits will be scheduled at 1, 3, 6, 12, 24 and 36 months post-surgery.

Study premature discontinuation details (any time from surgery till end of the study)

- Reason for premature discontinuation
- If possible, the following information to be collected: Adverse Events, Adverse Events of Special Interest, Comorbidities and their evaluation for the assessment of adverse events (AEs / AESI), Granuloma occurrence and Tissue adhesions and other clinically significant events for the endpoint
- Vital signs (as per each site's standard of care as blood pressure, body temperature, and heart rate), if available
- Laboratory data (as per each site's standard of care such as: blood count, C-reactive protein [CRP], International Normalized Ratio[INR], Activated Partial Thromboplastin Time [APTT]),if available

PasTel

Table 5 PasTel Study data collection schedule

Collected data (if available)	Screening	Surgery	Hospital Discharge Data (collected during perioperative period defined as standard practice discharge from the hospital after the surgery at the site)	Follow-up Visits/Contacts (months ²)						Study premature discontinuation details (any time from surgery till end of the study)
				1	3	6	12	24	36	
				Visit window: +/- 15 days			Visit window: +/- 30 days			
Informed consent	•									
Demographic Data	•									
Inclusion/Exclusion Criteria	•	•								
Underlying disease	•									
Type and date of surgery		•								
Patient's discharge details			•							
Co-morbidities and their evaluation for the assessment of adverse events (AEs / AESI)	•	•	•	•	•	•	•	•	•	
Concomitant medication	•	•	• ¹	•	•	•	•	•	•	
Specific treatments, such as: ECMO (extracorporeal membrane oxygenation), hypothermia , ECC (extracorporeal circulation), MI-ECC (minimized systems for extracorporeal circulation)		•								
TachoSil usage details		•								

PasTel

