10.4 DATA SOURCES

The study will utilize a data collection system implemented by the Sponsor, targeting patients who meet the eligibility criteria. Variables collected for the purpose of the study will be re-transcribed from existing electronic and/or paper medical records maintained at site. The PasTel study involves primary data collection in which the data collected are derived from routine clinical care. In instances where patient recruitment or follow-up activities specific to evaluating the safety of TachoSil exposure, extend beyond the regular routine activities at the study site, additional data will be collected by personnel at the participating study site. This primary data collection will be incorporated into the case report forms (CRFs)

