10.5 STUDY SIZE

Approx.4 or more, if required, paediatric surgery centres will participate in the PasTel study.

Based on feasibility assessments, approximately 66 patients are expected to qualify for the study and undergo surgery. All patients who undergo surgery will be included in the analysis. An anticipated dropout rate is 10 %.

The recruitment will be conducted until the planned number of patients is reached. All patients available in the study population will be considered for the analysis.

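### The loss-to-follow-up procedure relies on contact alone and does not call for a check of the site medical record, which is the study's own data source

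*Protocol*

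**What the plan says.** **Contact procedure.** Protocol section 10.2, under Lost-to-follow-up, lists one telephone call, up to two reminder calls, and then: "If there is still no response after three phone calls, the participant will be sent an email or certified letter". No further step follows. The same paragraph defines lost children as those who cannot be reached, with the consequence that their status is unknown and long-term information, adverse events included, cannot be collected. It contrasts them with dropouts, a term that "refers to patients who voluntarily withdraw from the study, with their health status known upon departure".

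**Collection points.** Section 10.3 gathers follow-up items at the visits or contacts scheduled for months 1, 3, 6, 12, 24 and 36. For premature discontinuation it plans one collection: "If possible, the following information to be collected: Adverse Events, Adverse Events of Special Interest", together with comorbidities, granuloma, adhesions and other endpoint events. Nothing is scheduled after it.

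**Data source.** Section 10.4: "Variables collected for the purpose of the study will be re-transcribed from existing electronic and/or paper medical records maintained at site". Section 10.3 says the same of the listed data.

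**Size and expected loss.** Section 10.2: "Estimated total number of recruited patients is 66"; "An anticipated dropout rate is 10" per cent; "Finally, number of subjects eligible for analysis: sample size is expected to be at least 60". It also aims for loss to follow-up below 10% and anticipates approximately 10%. Section 10.5: "All patients who undergo surgery will be included in the analysis".

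**The concern.** The procedure treats a family that cannot be reached as a child whose outcome cannot be learned. In a study that transcribes its data from the operating centre's chart, the one does not follow from the other. A child whose parents no longer answer may still return to that centre with an abscess, for imaging or for a second operation. Section 10.1 defines clinically significant reactions largely through re-intervention, medical treatment, findings at surgery and abnormal imaging. Such events usually leave an entry in a hospital record.

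At stake is a rare-event safety proportion over 36 months in a small cohort. If families of children with complications are more likely to stop responding, or less likely, the reported proportion is biased, and its confidence interval does not show this. Section 10.9 acknowledges attrition bias as a limitation but does not use the chart to reduce it.

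**Working it through.** **Inputs.** Recruited: 66 (section 10.2). Dropout: 10% (sections 10.2 and 10.5). Loss to follow-up: approximately 10% (section 10.2). Expected for analysis: at least 60 (section 10.2). The study is descriptive, with no hypothesis to be tested (Annex 2), so there is no power figure to check.

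**1. The plan's own figure.** 66 × (1 − 0.10) = 59.4, which agrees with 60 to within one child. In reverse, 60 × 1.10 = 66, and 60 / 0.90 = 66.7, so 67. The stated 60 is reproduced, and it allows for a single 10% loss.

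**2. Children without 36-month status.** The protocol gives dropout and loss to follow-up as differently defined losses of about 10% each and does not say whether they overlap.
- Same 10%: 66 × 0.10 = 6.6, so 6 to 7 missing and 59 to 60 observed.
- Separate and additive (assumption): 66 × 0.20 = 13.2, so 13 to 14 missing and 52 to 53 observed.

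**3. Bounds on the proportion among all 66.** With x observed events and m children missing, the proportion lies between x/66 (no missing child had an event) and (x + m)/66 (every missing child did).

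| Missing m | Bounds for x = 0 |
|---|---|
| 6 | 0% to 6/66 = 9.1% |
| 7 | 0% to 7/66 = 10.6% |
| 13 | 0% to 13/66 = 19.7% |
| 14 | 0% to 14/66 = 21.2% |

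These are limits, not forecasts.

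**4. Precision.** With zero events the exact two-sided 95% upper limit is 1 − 0.025^(1/n).
- n = 66: 5.4%
- n = 60: 6.0%
- n = 59: 6.1%
- n = 53: 6.7%

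Losing 7 children raises the limit by only 0.7 percentage points. The possible bias in step 3 is much larger than this loss of precision.

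**5. Which texts bear on record review after failed contact.** Section 10.2 gives contact steps only. Section 10.3 ties follow-up items to visits or contacts and adds one collection at discontinuation. Section 10.4 names the chart as the source in general terms. Section 12 requires all adverse events up to the final follow-up visit to be recorded. None of them tells a site to open the chart at a remaining scheduled time for a child who cannot be reached or has left.

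**The case against.** A reader might infer that data collection stops after the letter or at withdrawal. The documents do not say so. Section 10.1 follows all enrolled patients for up to 36 months. Section 12 requires adverse events to be recorded until the final visit and makes investigators responsible for identifying them. Section 10.3 plans an endpoint collection at discontinuation. A child who has not withdrawn and who reappears at the centre with a complication would fall under these duties. This part of the objection stands: the gap is the absence of a stated, scheduled record check, and there is no rule forbidding one.

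A reader might also infer that dropouts are treated as having known status at 36 months. The text limits the statement to the moment of departure and nowhere counts dropouts as event-free. How they enter the analysis is missing-data handling, which section 10.7 leaves to the statistical analysis plan. Nor can it be said that the consent form lacks an option to leave contact while allowing record use, because the consent pages are not in the text at hand.

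The protocol already does something about loss: it excludes children with a known risk of it, sets a contact sequence and discloses the limitation. The bounds above are also extreme. With 7 missing and no event among 59, five or more of the seven would need an event before the proportion among 66 (5/66 = 7.6%) passed the 6.1% upper limit.

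These points reduce the weight of the concern but do not close the gap. The general recording duties do not tell a site when to look for a child who has gone silent, and the loss-to-follow-up definition suggests there is nothing to collect. The analysis plan cannot recover outcomes that were never transcribed.

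**Conclusion.** The point holds as a gap in the retention procedure. It relies on contact alone and equates failed contact with uncollectable information, although the study's declared source is the site record. With 6 to 7 of 66 children missing, an observed proportion of zero is compatible with anything up to 9.1–10.6%; with 13 to 14 missing, up to 19.7–21.2%. The effect on precision is small, so the matter is possible bias.

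This rests on three assumptions: the protocol's own 10% figures, with their overlap unknown; some late events being treated at the operating centre; and consent allowing the record to be used. How many outcomes a chart check would recover cannot be derived from the documents. The conclusion does not extend to saying that collection ends at withdrawal or non-response, or that dropouts are counted as known at month 36.

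**What to change.** Amend the Lost-to-follow-up text in section 10.2 and the premature-discontinuation block in section 10.3 to state that:

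- for children who cannot be reached, and for those who withdraw from contact but whose consent still permits record use, site staff check the site record at each remaining scheduled time up to month 36 for endpoint events, re-operations and imaging findings;
- the contact attempt is repeated at those times;
- the date and source of the last known status are recorded;
- a child is classed as lost to follow-up only if neither contact nor a record entry is available.

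Full withdrawal of consent still ends collection. The sponsor should confirm that the consent form covers such record use before data collection starts, planned for 3Q 2026 (section 7).

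The cost is protocol wording and a short chart check for about 7 to 13 children. Events treated at other hospitals would still be missed, so the report should give the source of each late outcome.

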10.3 VARIABLES

For underlying disease and co-morbidities, diagnoses will be defined using Polish adaptation of ICD-10 codes. The exposure/dose will be defined as the number of patches of TachoSil applied during surgery. Concomitant medication will be coded according to the current version of World Health Organization (WHO) Drug Dictionary and Anatomical Therapeutic Chemical (ATC) coding. All adverse events reported during the study will be coded by System Organ Class (SOC) and preferred term (PT) using current version of MedDRA.

For the determination of the exposure, size and number of TachoSil patches will be used as a measure of dose. This method of exposure determination was used in previous clinical studies with TachoSil and is considered adequate to determine the dose of TachoSil used in a clinical setting during surgery. Duration of drug exposure is not considered relevant since TachoSil is a degradable medicinal product, and once applied it remains embedded in the wound until it degrades on its own. A detailed algorithm of exposure calculation will be provided in the study SAP.

For primary and secondary endpoints, rate of occurrence and cumulative incidence of AEs and AESIs will be determined: Time to onset (TTO), duration, severity, outcome, treatment and relatedness to TachoSil will be analyzed for reported AEs and AESI

The PasTel study is a prospective observational study with data collected from routine standard care practices. Data mentioned below will be re-transcribed from medical records and recorded in the eCRF.

Screening Visit

The following data will be collected:

Patient data:

PasTel_Study Protocol_en_V2.2 _2025 10 30
Confidential

PasTel

- Informed consent signature date
- Assessment of patient eligibility
- Demographic data collection (birthdate, age, gender)
- Medical history – underlying disease (date of initial diagnosis, disease name, use of treatments related to medical history)
- Comorbidities and their evaluation for the assessment of adverse events (AEs / AESI)
- Adverse Events evaluation including treatment of AEs
- Concomitant Medication
- Vital signs (as per each site's standard of care as blood pressure, body temperature, and heart rate), if available
- Laboratory data (as per each site's standard of care such as: blood count, C-reactive protein [CRP], International Normalized Ratio[INR], Activated Partial Thromboplastin Time [APTT]), if available

Surgery

- Data to be collected:
 - type and date and time of surgery
 - patient's discharge details
- Adverse Events evaluation including treatment of AEs
- Adverse Events of Special Interest evaluation including treatment of AESIs
- Comorbidities and their evaluation for the assessment of adverse events (AEs / AESI)
- TachoSil usage related data:
 - exposure/dose/application time (size and number of patches applied)
 - repeated application
 - treatment not effective/other treatment required
 - Batch number, expiration date and size of all TachoSil matrices used
 - The wound condition and application of the TachoSil matrix will be assessed and collected. The following wound data will be assessed and collected: wound location, amount of blood in the wound assessed by the surgeon. The following TachoSil matrix data will be collected: TachoSil matrix size, and application method (dry, pre-moistened).
- Concomitant medication(except drugs used for anaesthesia)
 - Specific treatments, such as: ECMO (extracorporeal membrane oxygenation), hypothermia, ECC (extracorporeal circulation), MiECC (minimal invasive systems for extracorporeal circulation),
- Vital signs (as per each site's standard of care as blood pressure, body temperature, and heart rate), if available
- Laboratory data (as per each site's standard of care such as: blood count, C-reactive protein [CRP], International Normalized Ratio[INR], Activated Partial Thromboplastin Time [APTT]),if available

Hospital Discharge Data

At the time of discharge following information should be collected and enter into eCRF:

PasTel

- Concomitant therapies updates
- Adverse Events evaluation including treatment of AEs
- Adverse Events of Special Interest evaluation including treatment of AESIs
- Comorbidities and their evaluation for the assessment of adverse events (AEs / AESI)
- Granuloma occurrence and Tissue adhesions and other clinically significant events for the endpoint
- Vital signs (as per each site's standard of care as blood pressure, body temperature, and heart rate), if available
- Laboratory data (as per each site's standard of care such as: blood count, C-reactive protein [CRP], International Normalized Ratio[INR], Activated Partial Thromboplastin Time [APTT]),if available

Follow-up Visits/Contacts

At the time of Follow Up Visits/Contacts following information should be collected and enter into eCRF:

- Concomitant therapies updates
- Adverse Events evaluation including treatment of AEs
- Adverse Events of Special Interest evaluation including treatment of AESIs
- Comorbidities and their evaluation for the assessment of adverse events (AEs / AESI)
- Granuloma occurrence and Tissue adhesions and other clinically significant events for the endpoint
- Vital signs (as per each site's standard of care as blood pressure, body temperature, and heart rate), if available
- Laboratory data (as per each site's standard of care such as: blood count, C-reactive protein [CRP], International Normalized Ratio[INR], Activated Partial Thromboplastin Time [APTT]),if available

Follow-up visits will be scheduled at 1, 3, 6, 12, 24 and 36 months post-surgery.

Study premature discontinuation details (any time from surgery till end of the study)

- Reason for premature discontinuation
- If possible, the following information to be collected: Adverse Events, Adverse Events of Special Interest, Comorbidities and their evaluation for the assessment of adverse events (AEs / AESI), Granuloma occurrence and Tissue adhesions and other clinically significant events for the endpoint
- Vital signs (as per each site's standard of care as blood pressure, body temperature, and heart rate), if available
- Laboratory data (as per each site's standard of care such as: blood count, C-reactive protein [CRP], International Normalized Ratio[INR], Activated Partial Thromboplastin Time [APTT]),if available

PasTel

Table 5 PasTel Study data collection schedule

Collected data (if available)	Screening	Surgery	Hospital Discharge Data (collected during perioperative period defined as standard practice discharge from the hospital after the surgery at the site)	Follow-up Visits/Contacts (months ²)						Study premature discontinuation details (any time from surgery till end of the study)
				1	3	6	12	24	36	
				Visit window: +/- 15 days			Visit window: +/- 30 days			
Informed consent	•									
Demographic Data	•									
Inclusion/Exclusion Criteria	•	•								
Underlying disease	•									
Type and date of surgery		•								
Patient's discharge details			•							
Co-morbidities and their evaluation for the assessment of adverse events (AEs / AESI)	•	•	•	•	•	•	•	•	•	
Concomitant medication	•	•	• ¹	•	•	•	•	•	•	
Specific treatments, such as: ECMO (extracorporeal membrane oxygenation), hypothermia , ECC (extracorporeal circulation), MI-ECC (minimized systems for extracorporeal circulation)		•								
TachoSil usage details		•								

PasTel

Adverse Events evaluation including treatment of AEs
Granuloma occurrence and Tissue adhesions and other clinically significant events for the endpoint ⁴	
AESIs evaluation including treatment of AESIs	
Vital signs ³
Laboratory values ³
Reason for premature discontinuation										.
1 - except drugs used for anaesthesia 2 – 1 month is defined as 30 days 3 – applicable during the follow period only if available 4 – The wound condition and application of the TachoSil matrix will be assessed and collected. The following wound data will be assessed and collected: wound location, amount of blood in the wound assessed by the surgeon. The following TachoSil matrix data will be collected: TachoSil matrix size, and application method (dry, pre-moistened).										

